## 14.3 Interim Analysis

No interim analysis is planned for the primary objectives in this study.

## 14.4 Primary Objective(s)

### 14.4.1 Primary Objective #1 (Effectiveness)

The primary objectives of this study are to demonstrate that the Medtronic Hugo™ RAS system is safe and effective when used for inguinal and ventral robotic hernia repair. The primary effectiveness endpoint is the surgical success rate, which is defined as the procedure not going into conversion.

The primary effectiveness hypothesis is to test if the surgical success rate is above the performance goal. A performance goal (PG) of 85% (100%-conversion rate) is pre-defined to evaluate the surgical success rate. Let  $P$  be the surgical success rate in this study. The statistical hypothesis is formulated as follows:

$$H_0: P \leq 85\% \text{ vs. } H_a: P > 85\%$$

The hypothesis will be tested using an exact binomial test at one-sided alpha of 0.025. The 95% two-sided confidence interval will also be reported; the confidence interval will be calculated using the Clopper-Pearson exact binomial method.

The analysis set for the primary effectiveness will be the full analysis set (FAS) for the combined inguinal and ventral hernia cohort, which will be further elaborated in **section 14.9**. If 5% of the data or fewer are missing for the primary analysis, no imputation will be used. Otherwise, missing data will be imputed for the FAS using multiple imputation. Sensitivity analysis will be performed for the primary effective

*Medtronic Business Restricted*

endpoint using available data with no imputation in FAS, PPAS as well as tipping-point analysis in FAS to evaluate the robustness of the study results. A summary of device-related conversions will be provided as well.

See **Table 13** below for the rationale supporting the 85% performance goal for the primary effectiveness endpoint. For details on the sample size calculation based on the primary effectiveness endpoint, see details in **Section 14.7**.

**Table 13: Primary Effectiveness Endpoint – Performance Goal Determination**

Primary Effectiveness Endpoint: Surgical Success Rate		
Surgery Type	Performance goal (PG)	Rationale
Inguinal and Ventral Hernia Repair	85%	The literature-based mean effect size for conversions is 1.5% with a 95% CI of 0.2% to 9.4%. The 95% prediction interval is 0.1% to 29.3%. A PG of 85% for the surgical success rate, equivalent to a 15% conversion rate, is set, which is aligned with the upper 95% CI with an added 5.6% margin and falls within the 95% prediction interval.

## 14.4.2 Primary Objective #2 (Safety)

The primary safety objective of this study is to demonstrate that the Medtronic Hugo™ RAS system is safe when used in inguinal and ventral hernia repair. The primary safety endpoint is the rate of subjects with one or more procedure- and/or device-related SSEs from the first incision through 30 days post-procedure.

The primary safety hypothesis is to test the overall 30-day procedure- and/or device-related SSEs rate (i.e., rate of subjects with one of more procedure- and/or device-related SSEs) against a performance goal. The performance goals are determined based on meta-analyses of published literature data.

Let  $R$  be the 30-day procedure- and/or device-related SSEs rate, and PG be the performance goal for a specific surgery group. The statistical hypothesis is formulated as follows:

$$H_0: R \geq PG \quad \text{vs.} \quad H_a: R < PG$$

The hypothesis will be tested using an exact binomial test at the significance level and the null hypothesis will be rejected if the p-value is significant comparing to alpha determined after multiplicity adjustment as described in **Section 14.12**. The 95% two-sided confidence interval will also be reported; the confidence interval will be calculated using the Clopper-Pearson exact binomial method.

The analysis set for the primary safety objective will be FAS with available data at 30 days, i.e., those subjects whose status (event, no event) at 30 days can be determined. The inguinal hernia cohort and ventral hernia cohort will be analyzed separately.

*Medtronic Business Restricted*

**CONFIDENTIAL**

056-F275 Rev G Clinical Investigation Plan Template

## Performance Goal Rationale

A literature search was performed to include each of the surgery types (inguinal hernia repair and ventral hernia repair) and both RAS and laparoscopic MIS procedure types. Point estimates along with 95% confidence intervals (CIs) and prediction intervals were calculated based on the reported literature data. Clinically meaningful margins and statistical precisions have been considered to determine the appropriate performance goals. The calculation details and rationales for the primary safety endpoint are summarized in **Table 14**.

**Table 14: Primary Safety Endpoint – Performance Goal Determination**

Primary Safety Endpoint: Rate of Subjects with One or More Procedure-/Device-Related Surgical Site Events (SSEs) through 30 Days Post-Procedure			
Surgery Type	Performance Goal (PG)	Sample Size	Rationale
Inguinal Hernia	30%	96	The literature-based maximum possible SSE rate is 3.8% with a 95% CI of 2.1% to 6.9%. The 95% prediction interval is 0.3% to 36.0%. A PG of 30% falls within the 95% literature-based prediction interval and is clinically relevant.
Ventral Hernia	30%	96	The literature-based maximum possible SSE rate is 4.5% with a 95% CI of 1.8% to 10.8%. The 95% prediction interval is 0.3% to 45.5%. A PG of 30% falls within the 95% literature-based prediction interval and is clinically relevant. Additionally, Medtronic-sponsored clinical study data show a 14.5% procedure- and/or device-related SSI+ SSO pooled rate, with a 95% CI of 8.8% to 22.0%. With an approximate 8% clinical margin added to the upper 95% confidence bound, these data support the PG of 30%.

## 14.5 Secondary Objective(s)

The secondary objective of this study is to demonstrate the Medtronic Hugo™ RAS system performs as intended when used in inguinal and ventral hernia repair. The secondary endpoints of this study will assess the overall performance of the Medtronic Hugo™ RAS system when used for the robotic surgery.

The following short-term secondary endpoints will be assessed through 30 days in all treated subjects:

- Complication rate: Overall rate of subjects with one or more procedure- and/or device-related complications (Clavien-Dindo Grade I or higher), from the first incision through 30 days post-procedure
- Major complication rate: Overall rate of subjects with one or more major procedure- and/or device-related complications (Clavien-Dindo Grade III or higher), from the first incision through

*Medtronic Business Restricted*

30-days post-procedure

- Operative time
- Readmission rate (through 30 days post-procedure): the proportion of subjects with any hospital readmissions through 30-days post-procedure
- Reoperation rate (through 30 days post-procedure): the proportion of subjects with any reoperation on the same target hernia through 30-days post-procedure
- Recurrence rate (through 30 days post-procedure): the proportion of subjects with any recurrences of hernia on the same anatomical region as the target hernia through 30-days post-procedure

The following long-term secondary endpoints will be assessed through 2 years in all treated subjects:

- Recurrence rate (through 2 years post-procedure): the proportion of subjects with any recurrences of hernia on the same anatomical region as the target lesion through 2 years post-procedure

The analysis set for the secondary objectives will be the FAS with available data. The secondary endpoints will be analyzed for the inguinal and ventral hernia cohort respectively.

Descriptive statistics will be used to summarize secondary endpoints. In addition, performance goals are pre-specified based on meta-analyses of published study data as well as considerations of clinically meaningful margins and statistical estimates (see details below and references in **Section 17.1**). Two-sided 95% confidence intervals will be provided as appropriate. The secondary objectives are not powered in this study. Instead, the secondary endpoints will be analyzed using descriptive statistics, which broadly negate the need for multiplicity adjustments. The role of the secondary endpoints is to explore additional effects and outcomes associated with either the procedure or the disease state. The pre-specified performance goals serve as benchmarks for interpretation rather than thresholds for statistical significance of clinical trial success in this study.

The performance goal details and rationales are summarized in **Tables 15 and 16** for short- and long-term secondary endpoints, respectively.

## Performance Goals for Short-term Secondary Endpoints (through 30 days post-procedure)

**Table 15: Short-term Secondary Endpoints – Performance Goal Determination**

Short-term Secondary Endpoints: through 30 Days Post-Procedure			
Endpoint	Surgery Type	PG	Rationale
Rate of subjects with any complications (through 30 days)	Inguinal Hernia Repair	40%	Only three cohorts of patients who underwent inguinal hernia repair and had data reporting on any complications CD grade I or higher were identified in the literature review. Thus, there were insufficient data to perform a statistical analysis. The upper 95% CI range for these three cohorts was 13.1 to 36.4%. A PG of 40%, which is approximately 4% above the range of upper limits of the individual cohorts and captures the complication rate for all three individual cohorts, would be clinically relevant for a descriptive comparison.
	Ventral Hernia Repair	40%	Only three cohorts of patients who underwent ventral hernia repair and had data reporting on any complications CD grade I or higher were identified in the literature review. Thus, there were insufficient data to perform a statistical analysis. The upper 95% CI range for these three cohorts was 9.2 to 78.8%. A PG of 40%, which falls within the range of upper limits of the individual cohorts and captures the complication rate for two of the three individual cohorts, would be clinically relevant for a descriptive comparison.
Rate of subjects with major complications (through 30 days)	Inguinal Hernia Repair	10%	Only one cohort of patients who underwent inguinal hernia repair and had data reporting on major complications CD grade III or higher was identified in the literature review. Thus, there were insufficient data to perform a statistical analysis. The upper 95% CI range for this cohort was 10.9%. A PG of 10%, which falls within the range of the upper limit of this individual cohort, would be clinically relevant for a descriptive comparison.

*Medtronic Business Restricted*

**CONFIDENTIAL**

056-F275 Rev G Clinical Investigation Plan Template

# Enable Hernia Repair Clinical Investigation Plan

MDT21022

Version 5.0

Page 75 of 116

Medtronic

	Ventral Hernia Repair	15%	Only three cohorts of patients who underwent ventral hernia repair and had data reporting on major complications CD grade III or higher were identified in the literature review. Thus, there were insufficient data to perform a statistical analysis. The upper 95% CI range for these three cohorts was 5.1 to 60.0%. A PG of 15%, which falls within the range of upper limits of the individual cohorts and captures the complication rate for two of the three individual cohorts, would be clinically relevant for a descriptive comparison.
Operative time (min)	Inguinal Hernia Repair	Unilateral Hernia Repair: 125 (min)	This analysis is based on 15 cohorts. The effect size index is the mean time. The random-effects model was employed for the analysis. The mean effect size is 80.9 min with a 95% CI of 70.7 to 91.0 min. If we assume that the true effects are normally distributed (in raw units), we estimate that the 95% prediction interval is 37.3 to 124.4 min. A PG of 125 minutes would be clinically relevant for a descriptive comparison.
		Bilateral Hernia Repair: 180 (min)	This analysis is based on 12 cohorts. The effect size index is the mean time. The random-effects model was employed for the analysis. The mean effect size is 109.6 min with a 95% CI of 91.8 to 127.4 min. If we assume that the true effects are normally distributed (in raw units), we estimate that the 95% prediction interval is 39.3 to 180.0 min. A PG of 180 minutes would be clinically relevant for a descriptive comparison.
	Ventral Hernia Repair	200 (min)	The analysis is based on nine cohorts. The effect size index is the mean time. The random-effects model was employed for the analysis. The mean effect size is 81.5 min with a 95% CI of 51.0 to 112.0 min. If we assume that the true effects are normally distributed (in raw units), we estimate that the 95% prediction interval is 0 to 196.8 min. A PG of 200 minutes would be clinically relevant for a descriptive comparison.
Readmission	Inguinal Hernia Repair	15%	The analysis is based on ten cohorts. The effect size index is the mean readmission rate. The mean effect size is 1.6% with a 95% CI of 1.0 to 2.7%. If we assume that the true effects are normally distributed (in raw units), we estimate that the 95% prediction interval is 0.9 to 3.0%. With a 12% clinical margin added, a PG of 15% would be clinically relevant for a descriptive comparison.

*Medtronic Business Restricted*

**CONFIDENTIAL**

056-F275 Rev G Clinical Investigation Plan Template

# Enable Hernia Repair Clinical Investigation Plan

MDT21022

Version 5.0

Page 76 of 116

Medtronic

rate (through 30 days post-procedure)	Ventral Hernia Repair	20%	This analysis was based on five cohorts. The effect size index is the mean readmission rate. The mean effect size is 11.0% with a 95% CI of 9.1 to 13.3%. If we assume that the true effects are normally distributed (in logit units), we estimate that the 95% prediction interval is 8.0 to 14.9%. With a 5% clinical margin added, a PG of 20% would be clinically relevant for a descriptive comparison.
Re-operation rate (through 30 days post-procedure)	Inguinal Hernia Repair	10%	Only two cohorts of patients who underwent inguinal hernia repair and had data reporting on reoperation rate through 30 days were identified in the literature review. Thus, there were insufficient data to perform a statistical analysis. The upper 95% CI range for these two cohorts was 10.9 to 16.8%. A PG of 10%, which falls below the upper limits of the individual cohorts, would be clinically relevant for a descriptive comparison.
	Ventral Hernia Repair	15%	Only two cohorts of patients who underwent ventral hernia repair and had data reporting on reoperation rate (one through 30 days, one through 90 days) were identified in the literature review. Thus, there were insufficient data to perform a statistical analysis. The upper 95% CI range for these two cohorts was 3.1 to 33.6%. A PG of 15%, which falls within the range of upper limits of the individual cohorts and captures the mean transfusion rate for both individual cohorts, would be clinically relevant for a descriptive comparison.
Recurrence rate (through 30 days post-procedure)	Inguinal Hernia Repair	8%	This analysis was based on five cohorts. The effect size index is the mean recurrence rate. The mean effect size is 0% with a 95% CI of 0.0 to 1.0%. Adding an approximate 7% clinical margin to the upper 95% CI bound, a PG of 8% would be clinically relevant for a descriptive comparison.
30 days post-procedure)			
	Ventral Hernia Repair	10%	Only one cohort of patients who underwent ventral hernia repair and had data reporting on recurrence rate through 30 days was identified in the literature review. Thus, there were insufficient data to perform a statistical analysis. The upper 95% CI range for this cohort was 7.7%. Adding an approximate 2% clinical margin, we set the PG at 10% for recurrence rate through 30 days following ventral hernia repair, which will be clinically relevant for a descriptive comparison.

*Medtronic Business Restricted*

**CONFIDENTIAL**

056-F275 Rev G Clinical Investigation Plan Template

## Performance Goals for Long-term Secondary Endpoints (through 2 years)

**Table 16: Recurrence Rate through 2 Years – Performance Goal Determination**

Long-term Secondary Endpoint: Hernia Recurrence Rate			
Endpoint	Surgery Type (Inguinal, Ventral Hernia)	PG	Rationale
Recurrence rate (through 2 years)	Inguinal Hernia Repair	15%	This analysis was based on eight cohorts. The effect size index is the mean recurrence rate. The mean effect size is 0.6% with a 95% CI of 0.2 to 1.3%. If we assume that the true effects are normally distributed (in logit units), we estimate that the 95% prediction interval is 0.2 to 1.7%. The PG for recurrence through 30 days is set at 8%. Adding a 7% clinical margin to the 30-day PG, we set the 2-year PG at 15% for reoperation rate through 2 years following inguinal hernia repair.
	Ventral Hernia Repair	37%	This analysis was based on seven cohorts. The effect size index is the mean recurrence rate. The mean effect size is 10.9% with a 95% CI of 4.7 to 23.1%. If we assume that the true effects are normally distributed (in logit units), we estimate that the 95% prediction interval is 1.3 to 53.6%. We set a PG of 37% recurrence rate through 2 years following ventral hernia repair, which falls between the upper bounds for the 95% CI and 95% prediction interval and is clinically relevant.

### 14.6 Ancillary Objective(s)

Descriptive analyses of other pre-specified outcome measures beyond the primary and secondary objectives will be exploratory in nature and are not intended as a focus of the study for the evaluation of the study device.

The following data will be collected as applicable:

- Estimated intraoperative blood loss
- Transfusion rate
- Hospital length of stay
- Mortality through 30 days
- Device- and procedure-related AEs through 2 years
- Readmission rate through 2 years

*Medtronic Business Restricted*

- Reoperation rate through 2 years
- Surgeon experience
- Pain scores at baseline, 30 days, and 3 months (ACHQC questionnaire)

The analysis set for these ancillary objectives will be the FAS with available data. The ancillary endpoints will be analyzed for the inguinal and ventral hernia cohort respectively.

## 14.7 Sample Size Determination

The sample size for the study was estimated based on the primary safety and effectiveness hypotheses.

The effectiveness hypothesis is to test if the surgical success rate is above the performance goal. Based on published data and clinical practice presented in **section 14.4.1**, the performance goal of the conversion rate is set to be 85% (100%-conversion rate). Assuming a success rate of 93%, a sample size of 172 subjects for the combined inguinal and ventral hernia cohort will provide 90% of power with one-sided alpha of 0.025. Calculation was performed using the PASS 2023. Account for 10% attrition rate, the enrollment is 192 subjects.

The primary safety objective is also part of the consideration for the sample size determination. The primary safety endpoint is the rate of subjects with any procedure- and/or device-related SSEs from the first incision through 30 days post-procedure. A statistical hypothesis with a performance goal is specified for each of the two surgery types (inguinal hernia repair and ventral hernia repair). The sample size for each surgery type is 96 with up to 192 subjects in total, after accounting for an estimate 10% attrition rate. For details, refer to **section 14.4.2**.

With the consideration of both the effectiveness and safety primary objectives, up to a total of 192 subjects are planned to be enrolled in this study. Up to ten study sites will be used. To keep enrollment balanced, a single study site will be allowed to treat no more than 30% of the total population.

## 14.8 Demographics and Baseline Characteristics

The number of subjects screened, treated, discontinued during the study, as well as the reasons for discontinuations will be summarized for all centers combined and each center separately. Disposition and reason for study discontinuation will also be provided as a by-subject listing. All demographics and baseline characteristics will be summarized using descriptive statistics.

## 14.9 Analysis Populations

The following populations will be considered for the analysis of data for this study:

### Enrolled Analysis Set

All subjects who signed the informed consent.

### Full Analysis Set

The full analysis set (FAS) is defined as all enrolled subjects in whom the Hugo™ RAS procedure is begun, defined as the first skin incision. This is also known as a modified intent-to-treat population. If a subject is

*Medtronic Business Restricted*

consented, but the first incision does not occur (e.g., if the subject becomes ineligible during the timeframe between consent and the procedure day), that subject will not be considered part of the FAS. The FAS will be the primary analysis set for the evaluation of the primary and secondary endpoints as appropriate. The analysis sets for various study endpoints are detailed in **Section 14.4** through **Section 14.5**.

AEs will be collected from the time of consent. AEs occurring in subjects excluded from the FAS will be followed post-consent through study exit and will be reported in a listing in the clinical study report. These AEs will not be included in the primary FAS analysis for either AE reporting or the analysis of the primary and secondary endpoints. The number and proportion of subjects experiencing each type of adverse event will be summarized by site and overall, for the FAS.

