### 5.2 Endpoints

#### 5.2.1 Primary Endpoints

The primary effectiveness endpoint is the surgical success rate defined as the procedure not going into conversion. Conversion is defined as the switch from the robotic-assisted approach using the Hugo™ RAS system to laparoscopic, open surgery, or use of an alternative robotic-assisted system.

Procedural steps that are usually performed without robotic assistance per standard of care, including but not limited to mesh insertion, suture needle removal, or tacking, are not considered a conversion and will not contribute to the primary effectiveness endpoint.

The primary safety endpoint is the overall rate of subjects with one or more study procedure- and/or device-related surgical-site events (SSEs), from the first incision through 30 days post-procedure. SSE is defined as the following complications:

*Medtronic Business Restricted*

- Surgical-site occurrence (SSO):
  - Bleeding, Hemorrhage: Requiring transfusion
  - Bowel Injury
  - Bowel Obstruction
    - Note: Functional obstruction associated with general anesthesia and/or pain killer drugs (opioids) is excluded for this endpoint
  - Cellulitis
  - Epigastric Vessel Injury
  - Symptomatic Hematoma: Requiring procedural intervention
  - Symptomatic Seroma: Requiring procedural intervention
  - Symptomatic Edema: Requiring procedural intervention
    - Note: Procedural intervention is defined as percutaneous drainage, wound opening or debridement, suture excision, or mesh removal (partial or total)
- Surgical-site infection (SSI): Infection occurring where the surgery took place, including superficial, deep, and organ space infections (standardized definition developed by the CDC)

The relatedness of the SSEs being classified as “procedure- and/or device-related” may include three scenarios: (1) only procedure-related SSEs, (2) only device-related SSEs, and (3) SSEs that are both procedure- and device-related. In this study procedure-relatedness refers to an AE that occurs due to the hernia repair procedure with the Hugo™ RAS system, and device-relatedness refers to an AE that results from the presence or performance (intended or otherwise) of the Hugo™ RAS system.

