### **7.1.3 Hugo™ RAS Arm Cart Assembly**

The arm carts consist of movable platforms with casters, each supporting a modular and extendable arm. Up to four arm carts can be connected to the system tower for simultaneous use during RAS. The arm carts are portable and easily movable within the operating room and the hospital. Prior to surgery, the OR team positions the arm carts around the surgical table according to the surgical procedure. The team can adjust the arm carts and arms to accommodate subject positioning and optimize bedside access to the

*Medtronic Business Restricted*

subject.

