7.1.3 Analysis Sets

The following populations will be considered for the analysis of data for this study. All enrolled subjects will be included in a subject disposition table indicating reasons for exclusion from each analysis set.

Enrolled Analysis Set

All subjects who signed informed consent.

Full Analysis Set

The full analysis set (FAS) is defined as all enrolled subjects in whom the Hugo™ RAS procedure is begun, defined as the first skin incision. If a subject is consented, but the first incision does not occur (e.g., if the subject becomes ineligible during the timeframe between consent and the procedure day), the subject will not be considered part of the FAS. The FAS will be the primary analysis set for the evaluation of the primary, secondary, and ancillary endpoints. In the case of missing data with no imputation, some subjects may be excluded from an objective analysis using the FAS analysis set. Consider imputation plans defined in section 7.4.

Per Protocol Analysis Set

The per protocol analysis set (PPAS) is a subset of the FAS including only those subjects without any major protocol deviations. Major deviation reasons include “Enrolled subject did not meet enrollment criteria” and “Unauthorized use of investigational device.” Reasons for exclusion of subjects from PPAS will be documented in the CSR.

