7.9.1.6 Determination of Subjects/Data for Analysis

The analysis set for the primary effectiveness will be the full analysis set (FAS) for the combined inguinal and ventral hernia cohort. If 5% of the data or fewer are missing for the primary analysis, no imputation will be used. Otherwise, missing data will be imputed for the FAS using multiple imputation.

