7.10 Safety Evaluation

Additional summaries of safety will be assessed for the FAS population. These include summaries of adverse events and device deficiencies (DD). AEs and DDs will be summarized with number of events, number of subjects who experienced the event, and percentage of subjects who experienced one or more events.

AEs for all subjects will be collected from consent through the study exit. AEs and DDs will be coded and summarized using the most recent version of Medical Dictionary for Regulatory Affairs (MedDRA). Serious Adverse Events (SAE), deaths, and Surgical Site Events (SSEs) will be adjudicated by an independent CEC as defined in the CIP. Cases where the investigator's classification does not match CEC's adjudication classification, both determinations will be provided within the final report; however, the CEC's adjudication will be used for data analysis.

AEs occurring in subjects excluded from the FAS will be followed post-consent through study exit and will be reported in the CSR. These AEs will not be included in the FAS summary analysis for either AE reporting or the analysis of the primary and secondary endpoints.

For the FAS, AEs will be reported by the type (preferred term), seriousness, and procedure/device relatedness. Summaries will focus on the time periods which are complete as of the snapshot for the report, with special attention to those periods which start during the procedure (e.g. during the procedure to 30 days after the procedure).

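### A case cancelled before first incision because of a Hugo fault is in neither the effectiveness rate nor the SAP device-deficiency summary, and a repair started another way after such a fault is not classified

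*Protocol*

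**What the plan says.** The Protocol (14.9) and the SAP (7.1.3) define the FAS identically, as "all enrolled subjects in whom the Hugo™ RAS procedure is begun, defined as the first skin incision". Both add that the subject is outside the FAS in this case: "If a subject is consented, but the first incision does not occur". The one example given is loss of eligibility between consent and the day of surgery. Neither document mentions a non-start caused by the device.

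On effectiveness, SAP 7.9.1.6 states: "The analysis set for the primary effectiveness will be the full analysis set (FAS) for the combined inguinal and ventral hernia cohort". The sensitivity analyses in SAP 7.9.1.7.1 use the FAS (imputed or available data, and a tipping-point analysis) or the per-protocol set, which is a subset of the FAS. Conversion is defined in Protocol 5.2.1 without a time point: "Conversion is defined as the switch from the robotic-assisted approach using the Hugo™ RAS system to laparoscopic, open surgery", or to an alternative robotic system.

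On device deficiencies, Protocol 12.2 collects them throughout the study, and Table 7 lists them from the screening visit. Protocol 14.15 says they will be summarised and does not limit that summary to the FAS. SAP 7.10 does: "Additional summaries of safety will be assessed for the FAS population", with device deficiencies named among those summaries. For subjects outside the FAS, both documents carry adverse events into the report but do not mention device deficiencies.

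There is a period in which a set-up fault can occur before incision. Protocol 7.1.3 says "Prior to surgery, the OR team positions the arm carts around the surgical table according to the surgical procedure", Table 7 records robot set-up time, and Protocol 10.1.2 starts the operation at first incision.

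**The concern.** A fault that forces a switch just after incision is a conversion and counts against the device. The same fault just before incision, if it leads to cancellation, removes the subject from numerator and denominator. This exclusion can depend on how the device performs. Within the effectiveness rate it can act in only one direction, because the subjects removed would otherwise be failures. The ineligibility example does not have this property.

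Two things are at stake. One is the completeness of the device-performance account in a single-arm pivotal study. A set-up failure that harms nobody produces no adverse event, so the adverse-event listing for non-FAS subjects would not show it, and SAP 7.10 leaves it out of the deficiency table. The other is reproducibility. Where the team operates another way from the outset, two programmers could classify the subject differently, and the choice would then be made with the data in hand.

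**Working it through.** **Which analyses reach the subject**

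| Planned output | Population | Includes a pre-incision cancellation? |
|---|---|---|
| Primary effectiveness (SAP 7.9.1.6) | FAS | No |
| Sensitivity analyses (SAP 7.9.1.7.1) | FAS or per-protocol subset | No |
| Device-deficiency summary (SAP 7.10) | FAS | No |
| Device-deficiency summary (Protocol 14.15) | Not limited to FAS | Not excluded |
| Disposition and discontinuation (Protocol 14.8, 14.9; SAP 7.1.1, 7.1.3) | All enrolled | Yes, as a reason |

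**Reproducing the plan's figure.** Inputs from SAP 6: n = 172, goal 85%, expected success 93%, one-sided alpha 0.025. Protocol 14.4.1 specifies an exact binomial test. Let X be the number of conversions.

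- P(X ≤ 16 | 172, 0.15) = 0.0189 and P(X ≤ 17 | 172, 0.15) = 0.0331, so at most 16 conversions pass.
- Power is P(X ≤ 16 | 172, 0.07) = 90.4%, which agrees with the stated 90%.

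**Counting pre-incision failures.** With f conversions in 172 FAS subjects and k added failures, p = P(X ≤ f + k | 172 + k, 0.15).

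| f of 172 | Largest k that still passes | Smallest k that fails |
|---|---|---|
| 16 | 0 (p = 0.0189) | 1: 17/173, p = 0.0310 |
| 14 | 2: 16/174, p = 0.0164 | 3: 17/175, p = 0.0271 |
| 12 (planned: 0.07 × 172 = 12.04) | 5: 17/177, p = 0.0236 | 6: 18/178, p = 0.0376 |
| 3 (literature mean 1.5%: 0.015 × 172 = 2.6) | 15: 18/187, p = 0.0208 | 16: 19/188, p = 0.0330 |

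At a true success rate of 93%, the chance of exactly 16 conversions in 172 is 5.5%. The single-case reversal is therefore a boundary result.

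**Scenario at the performance goal (assumed rates).** Suppose failure among all attempted Hugo cases is exactly 15%, and a share s of attempted cases fails before incision and is excluded. The FAS failure rate is then (0.15 − s)/(1 − s). The chance of passing with 172 FAS subjects is:

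| s (assumed) | FAS failure rate | Chance of passing |
|---|---|---|
| 0 | 15.0% | 1.9% |
| 1% | 14.1% | 3.8% |
| 2% | 13.3% | 7.3% |
| 3% | 12.4% | 13.2% |

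**Scenario at the planned rate (assumed rates).** If 93% succeed after incision and a share q of 172 attempted cases fails before it, success over all attempted cases is 0.93 × (1 − q). The chance that the all-attempted rate meets the goal is 90.4%, 79.4%, 64.5% and 47.9% for q = 0, 1, 2 and 3%.

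**The case against.** The strongest reply is that the endpoint concerns conversion of a procedure. A cancelled subject has had no procedure to convert and may have a Hugo repair later. The 85% goal was built from conversions reported during robotic repair (Protocol 6.2.2, Table 13), so adding cancelled cases brings in a failure type that the benchmark is not stated to include. Protocol 14.9 openly calls the FAS a modified intent-to-treat population. This stands. It is why the FAS should remain primary and the added analysis should be supporting only.

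A reader might infer that every set-up fault followed by another approach drops out of the FAS. The text does not establish that. Such a subject does have a skin incision, the conversion definition carries no time point, and the derivation in SAP 7.9.1.2 turns on the site reporting that the surgical plan was not followed and the case was converted. The subject could be read as in the FAS and a conversion, or as outside because no Hugo procedure began. Only cancellation before any incision is clearly excluded.

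A reader might also infer that these cases would be hidden. They would not be. Disposition tables give exclusion reasons, discontinuations are listed by subject, and deficiencies are still reported to the sponsor. The FAS limit on the deficiency table comes from SAP 7.10 alone, although SAP 7.11 declares no change from the Protocol.

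Finally, nothing in the documents shows that sites differ in when they set up relative to incision. A fault after incision is already counted if it causes a switch.

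**Conclusion.** The gap is real but limited. A Hugo-caused cancellation before incision is absent from the success rate, from all its planned sensitivity analyses and from the SAP's deficiency summary. The status of a repair begun another way after a set-up fault is undefined. No figure in the plan is wrong.

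The size rests on a pre-incision failure rate that the documents do not give. On the exact test with 172 subjects, reversing a pass takes one such case at 16 conversions, three at 14, six at the planned 12, and 16 at the literature mean.

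It would be tempting to read the 3.8%, 7.3% and 13.2% pass probabilities as an inflated type I error of the trial. They are not: the documented hypothesis is about conversion in the FAS, and its exact error is 1.9%. Those figures apply only to success among all attempted cases, under assumed rates and a true value exactly at the goal. The point should be addressed because the remedy is cheap and the exclusion can only favour the device. It does not invalidate the primary test.

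**What to change.** Keep the FAS, alpha, sample size and success criterion as they are, and make three changes to the SAP before the analysis.

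1. **7.1.3 and 7.9.1.2:** state whether a subject operated on from the outset by another approach after a Hugo set-up fault is in the FAS as a conversion or is excluded.
2. **7.9.1.7.1:** add one supporting analysis that takes the FAS plus subjects in whom the planned Hugo repair was abandoned before incision because of a Hugo device or set-up fault, and counts the added subjects as failures. Identify them from the FAS-exclusion reason and the device-deficiency form. Leave out scheduling and logistics reasons. Note beside the result that the 85% goal was derived from conversions during robotic surgery.
3. **7.10:** report device deficiencies for all enrolled subjects, with those outside the FAS in a separate row. This also brings the SAP into line with Protocol 14.15.

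The cost is SAP wording, one extra analysis and one table row, from records already planned. The exclusion reason must be specific enough to separate a device fault from logistics. The downside is that the supporting success rate may be slightly lower than the primary one. If no such case occurs, the row reads zero.
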